7.2.3. Recommended Phase 2 Dose Determination

The RP2D will be a dose at which at least 10 patients, but no more than 20, have been enrolled. The RP2D will be agreed upon following discussion between the investigators and the Lilly CRP or CRS and will include an assessment of safety, PK, and PD data. At the RP2D, the intersection of the number of patients dosed and the number of DLTs at that dose level on the mTPI grid should indicate “S” or “E.”

7.2.4. Monitoring and Treatment Guidance for the Investigator

7.2.4.1. Infusion-Related Reactions

Due to the risk of hypersensitivity reactions with any biological agents, all patients should continue to be closely monitored for signs and symptoms indicative of an infusion-related reaction both in the acute period (immediately or within 24 hours after dosing) and up to several days to a few weeks after dosing for delayed reactions. In Cycles 1 and 2, acute assessments should include an assessment of vital signs starting at the time of initiation of the infusion and continuing until at least 60 minutes after the end of the infusion. At a minimum, vital signs should be obtained prior to infusion, during infusion, and at 1 hour post-infusion. The exact frequency of the monitoring is left to the discretion of the investigator. Monitoring should be performed in an area where resuscitation equipment and other agents (eg, epinephrine, corticosteroids) are readily available.

Per the CTCAE v 4.03 definition of infusion-related reactions, symptoms occurring during or following infusion of investigational therapy may be defined according to AE categories such as allergic reaction, anaphylaxis, or cytokine release syndrome. In the setting of symptoms occurring during or following infusion of investigational therapy, investigators are encouraged to

use the AE term “Infusion-related Reaction” and any additional terms (including those not listed here) that best describe the event.

Section 7.2.5 and Table JNBA.4 detail the treatment recommendations for LY3164530 infusion-related reactions. If a patient should have an infusion-related reaction to LY3164530, all attempts should be made to obtain an anti-LY3164530 antibody blood sample (immunogenicity sample) as close to the onset of the event as possible, at the resolution of the event and 28 days following the event. In addition, these same samples may be assessed for levels of LY3164530 and for PD markers to provide information on the nature of the infusion-related reaction. Immunogenicity samples will be collected during the follow-up visit for all patients. The procedure for sample collection and handling is described in a separate procedural manual.

If infusion-related reactions are observed, premedication with diphenhydramine hydrochloride (or equivalent), dexamethasone (or equivalent), or other medications as medically indicated may be considered for future patients. The decision to implement premedication for drug administration in subsequent patients will be made following a discussion between the investigators and Sponsor and will be documented in writing.

7.2.4.2. Skin Reactions

Skin rash is a known toxicity of EGFR inhibitors, and skin effects were observed with LY3164530 in a 5-week repeat-dose toxicity study in monkeys. In Study JNBA, skin reactions were observed at all dose levels with Schedule 1 and were dose limiting at 1250 mg. As a result, prophylaxis is permitted for the initial dose of LY3164530. Institutional-approved standard of care premedication for EGFR inhibitors, such as dexamethasone and/or topical and/or oral antibiotics, may be administered for the initial and subsequent doses.

Section 7.2.4.1 and Table JNBA.4 detail the treatment recommendations for LY3164530 skin reactions.

7.2.5. Dose Delays and Adjustments

7.2.5.1. Dose Delays and Omissions

The following rules should guide dosing:

- Before each cycle of LY3164530 the following parameters are required:
 - Hematologic: ANC $\geq 1.5 \times 10^9/L$, platelets $\geq 75 \times 10^9/L$, and hemoglobin ≥ 8 g/dL.
 - Non-hematologic: AEs must resolve to CTCAE v 4.03 Grade ≤ 1 , or baseline. Exceptions will be made for: alopecia, fatigue, skin reactions, or other toxicities that can be controlled with standard treatment; these toxicities must resolve to \leq Grade 2.
- The start of a cycle is the date of the Day 1 dose.
 - For Schedule 1: If the Day 15 dose cannot be administered within 21 days of the prior dose (by Day 22), it should be omitted. The interval between LY3164530 doses must not

be less than 14 days. If a dose is delayed (for toxicity or other circumstances), the next dose should be adjusted so that there is at least a 14-day interval.

–

For Schedule 2: If a dose cannot be administered within 10 days of the prior dose, it should be omitted. The interval between LY3164530 doses must not be less than 7 days. If a dose is delayed (for toxicity or other circumstances), the next dose should be adjusted so that there is at least a 7-day interval. If a dose cannot be administered within 28 days of the prior dose due to an AE, the patient should be removed from study drug treatment and should complete subsequent follow-up ([Table JNBA.4](#)).

- If the patient has completed the initial on-study radiographic assessment (eg, at the end of Cycle 2) and is continuing to receive benefit from therapy, delays of greater than 28 days may be acceptable if agreed upon by both the investigator and Sponsor. For instance, if a patient has a non-drug-related AE such as prolonged flu, the patient may continue on therapy if, in the opinion of the investigator, he/she is showing benefit from therapy and has recovered sufficiently from the AE.
- A delay of no more than 7 days because of holidays, weekends, inclement weather, or other justifiable events will be permitted and will not be counted as a protocol deviation.

7.2.5.2. Dose Adjustments

Dose adjustments should follow the guidance in [Table JNBA.4](#).

For patients requiring dose reductions, reescalation to the original assigned LY3164530 dose is not allowed. The patient must be maintained at a reduced dose level for all remaining cycles.

Table JNBA.4. Dose Modifications and Treatment Alterations in Patients Treated with LY3164530

Toxicity	CTCAE Grade	Recommendations
Infusion-related reaction	Grade 1 First occurrence	Decrease the LY3164530 infusion rate by 50% and monitor closely for any worsening. For subsequent infusions, premedicate with diphenhydramine hydrochloride; additional premedication may be administered at the investigator's discretion.
	Grade 2 First occurrence	Stop LY3164530 infusion. Administer diphenhydramine hydrochloride and acetaminophen for fever and oxygen. Resume infusion at 50% of previous rate once infusion-related reaction has resolved or decreased to Grade 1 in severity, and monitor closely for any worsening. For subsequent infusions, premedicate with diphenhydramine hydrochloride; additional premedication may be administered at the investigator's discretion. The reduced rate should be used for all subsequent infusions.
	Grade 1 or 2 Second occurrence	Administer dexamethasone. For subsequent infusions, premedicate with diphenhydramine hydrochloride, acetaminophen, and dexamethasone. The reduced infusion rate should be used for all subsequent infusions.
	≥Grade 3	Stop LY3164530 infusion immediately and disconnect infusion tubing from the patient. Administer diphenhydramine hydrochloride, dexamethasone, bronchodilators for bronchospasm, and other medications/treatment as medically indicated. Patients must not receive any further LY3164530 treatment.
Skin reactions (eg, acne-like rash)	Grade 3 First occurrence	Delay or omit LY3164530 treatment until ≤Grade 1 following the rules in Section 7.2.5.1. Treatment with topical and/or oral antibiotics should be considered.
	Grade 3 Second occurrence	Delay or omit LY3164530 treatment until ≤Grade 1 following the rules in Section 7.2.5.1. Dose reduce to the dose level used for the previous cohort for second occurrence. Treatment with topical and/or oral antibiotics should be considered.
	Grade 3 Third occurrence Or Grade 4	Patients must not receive any further LY3164530 treatment.
Other toxicities	≥Grade 3 First occurrence	Delay or omit LY3164530 treatment until ≤Grade 1 or baseline following the rules in Section 7.2.5.1. Based on the investigator's discretion, the full dose of LY3164530 may be administered or the dose may be reduced to the next lowest dose level. If event recurs at same grade, then dose reduce LY3164530 to the next lowest dose.
	≥Grade 3 Second occurrence	Delay or omit LY3164530 treatment until ≤Grade 1 or baseline following the rules in Section 7.2.5.1. If event recurs at same grade, then dose reduce LY3164530 to the next lowest dose. Exceptions may be made for transient changes in electrolytes that respond to treatment.

Abbreviation: CTCAE = Common Terminology Criteria for Adverse Events.

Note: In addition, the dose may be reduced to the next lower level for any toxicity at the discretion of the investigator.

7.3. Method of Assignment to Treatment

Patients who meet all criteria for enrollment will be assigned to receive LY3164530 in this study. Before each patient's enrollment into the study, an eligibility check must be conducted between the investigational site and the Lilly clinical research personnel to confirm that each patient meets all enrollment criteria. Upon confirmation of eligibility, the Sponsor will confirm the dose, schedule, infusion duration, and identification number assignment for each patient.

7.4. Blinding

This is an open-label study.

7.5. Concomitant Therapy

In the absence of clinical experience with LY3164530, patients should be closely evaluated to ensure identification of exacerbations of known side effects of concomitant medications. These should be reported immediately to the Sponsor. No other chemotherapy, radiotherapy, immunotherapy, herbal supplements intended to treat the cancer, cancer-related hormone therapy, or experimental drugs will be permitted while the patients are on this study. An exception will be made for prostate cancer patients continuing GnRH agonist therapy or breast cancer patients continuing antiestrogen therapy (eg, an aromatase inhibitor). However, the treatment should have been started at least 3 months prior to first dose of study drug. Patients on stable doses of bisphosphonates or denosumab are allowed to continue. These agents should not be initiated within the 4 weeks prior to study enrollment or at any point while on the study. Palliative radiotherapy of no more than 14 calendar days to a solitary (non-skull) skeletal metastasis will be permitted following discussions between the investigators and the Sponsor, so long as the skeletal metastasis is not the primary measurable lesion and the patient has not developed another reason for study discontinuation.

In addition, any disease progression requiring other forms of specific antitumor therapy will necessitate early discontinuation from the study. Appropriate documentation for all forms of premedications, supportive care, and concomitant medications must be captured on the case report form (CRF). Replacement hormonal therapy initiated before study entry will be allowed.

Patients should receive full supportive care during the trial. Routine prophylactic use of granulocyte colony-stimulating factors (G-CSF) is not permitted during this study. Should the use of hematopoietic colony-stimulating factors (CSFs) be necessary, follow the American Society of Clinical Oncology (ASCO) recommendations for the use of CSFs (Smith et al. 2015).

Erythropoietin and packed red blood cell (RBC) transfusion may be used according to ASCO guidelines (Rizzo et al. 2008) if clinically indicated at any time during the study. Platelet transfusions may be used according to ASCO guidelines (Schiffer et al. 2001).

All concomitant medications, including premedication, should be recorded throughout the patient's participation in the study on the electronic case report form (eCRF).

7.6. Treatment Compliance

LY3164530 will be administered intravenously at the investigational site, under the direction of the investigator. As a result, a patient's compliance with study drug administration is ensured. Patients should attend scheduled clinic visits and must comply with study criteria under their control. Deviation(s) from the prescribed dosage regimen should be recorded on the eCRF.

7.6.1. Evaluable Patients

Patients who withdraw from the study before receiving study drug will be replaced and will not be included in the safety or efficacy assessments. Safety analyses will be conducted on all patients who have been exposed to study drug, regardless of whether they are deemed evaluable for the assessment of a dose level.

Any patient who is discontinued from the study before completing 1 cycle of LY3164530 treatment will be deemed non-evaluable for assessment of a dose level, unless they experience a DLT prior to withdrawal. However, patients who receive all doses of LY3164530, but discontinue from study drug before the end of Cycle 1, will be considered evaluable for the assessment of a dose level, provided it can be documented whether the patient experienced a DLT during Cycle 1.

If the patient is noncompliant during Cycle 1 due to reasons other than drug-related toxicity, he or she will be considered non-evaluable and may be replaced.

Patients that require a dose reduction or omission during Cycle 1 or have a dosing delay of more than 3 days for reasons other than a study drug-related AE may be deemed non-evaluable for DLT assessment.

Nonevaluable patients may be replaced to ensure that enough patients complete 1 cycle of therapy at each dose level, unless accrual to that cohort has stopped due to a DLT.

Patients who are not evaluable for PK, but who complete 1 cycle of therapy, may be replaced upon consultation with the investigator(s) and the Lilly CRP or CRS to ensure adequate PK data, unless accrual to that cohort has stopped due to a DLT.

8. Safety, Pharmacokinetic, Pharmacodynamic, and Efficacy Data Collection

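### Protocol 7.6.1 protects an observed DLT under only one of its three routes to non-evaluability, so a patient with a Cycle 1 DLT and an unrelated deviation can be dropped from the dose-level assessment

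*Protocol*

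**What the plan says.** Protocol 7.6.1 (Evaluable Patients) gives three routes by which a treated patient becomes non-evaluable for the dose level:

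1. **Early discontinuation.** A patient discontinued before completing one cycle "will be deemed non-evaluable for assessment of a dose level, unless they experience a DLT prior to withdrawal".
2. **Noncompliance.** The rule applies if a patient is "noncompliant during Cycle 1 due to reasons other than drug-related toxicity, he or she will be considered non-evaluable and may be replaced". It is mandatory and mentions no DLT.
3. **Dosing deviation.** This covers patients who need a dose reduction or omission in Cycle 1, or who "have a dosing delay of more than 3 days for reasons other than a study drug-related AE may be deemed non-evaluable for DLT assessment". It is discretionary. It mentions no DLT and does not say who decides, on what grounds, or when.

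The same section allows replacement of non-evaluable patients "unless accrual to that cohort has stopped due to a DLT". It keeps every exposed patient in the safety analyses, "regardless of whether they are deemed evaluable for the assessment of a dose level". Section 7.4 states that the study is open label.

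Protocol 7.2.5.1 adds: "A delay of no more than 7 days because of holidays, weekends, inclement weather, or other justifiable events will be permitted". Such delays are not protocol deviations.

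The escalation rules use different words for the count. Section 7.2.2.3 and the RP2D rule in Section 7.2.3 refer to patients dosed, and Figure JNBA.1 to patients treated. None of them mentions evaluability. SAP 6.3 lists only early discontinuation (with the DLT exception) and non-evaluability for PK. It neither repeats nor repairs routes 2 and 3.

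**The concern.** A DLT in a patient who received no more drug than planned is evidence that the dose is toxic. Routes 2 and 3, followed as written, allow that evidence to be set aside when the patient also had an unrelated deviation.

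The situation can arise in ordinary conduct. Take a Schedule 1 patient whose Day 15 dose is given on Day 20 because of a holiday and who has a DLT on Day 24. The 5-day delay is permitted by Section 7.2.5.1 and falls before the Day 22 limit for that dose, yet it exceeds 3 days and so opens route 3. On Schedule 2, a dose not given within 10 days of the prior one is omitted. A logistical slip of more than 3 days on a 7-day interval can thus become an omission, which also opens route 3.

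At stake is the count that drives escalation and the RP2D condition (10 to 20 patients and a grid cell of S or E). With small cohorts, one patient can change the cell.

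**Working it through.** **Inputs.** Target DLT rate 30% and equivalence interval (0.287, 0.301), from Protocol 7.2.2.3. Unit-probability-mass rule from Protocol Attachment 7. The prior and the cut-off for DU are not stated; I assume Beta(1,1), and DU when P(p > 0.30 | data) > 0.95.

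**Reproducing Figure JNBA.1.** With x DLTs in n patients the posterior is Beta(1+x, 1+n−x). Each interval's probability is divided by its length, and the largest result gives E, S or D.

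*Example, 2/3.* The posterior is Beta(3,2), with F(p) = 4p³ − 3p⁴.
- F(0.287) = 0.0742 and F(0.301) = 0.0845.
- Under: 0.0742/0.287 = 0.26.
- Proper: (0.08446 − 0.07421)/0.014 = 0.73.
- Over: (1 − 0.0845)/0.699 = 1.31, the largest, so D.
- P(p > 0.30) = 1 − (0.1080 − 0.0243) = 0.916, below 0.95, so not DU.

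All 125 cells in rows 0 to 6 match the figure. Cut-offs of 0.90 and 0.93 give 8 and 2 mismatches. Rows 7 and above are broken in the extracted text and were not scored.

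**Effect of dropping one DLT patient.** Removal alone moves x/n to (x−1)/(n−1). Replacement by a DLT-free patient moves it to (x−1)/n.

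| All counted | Removed, not replaced | Removed and replaced |
|---|---|---|
| 1/3 S | 0/2 E | 0/3 E |
| 2/3 D | 1/2 S | 1/3 S |
| 3/4 DU | 2/3 D | 2/4 S |
| 2/6 S | 1/5 S | 1/6 E |
| 4/6 DU | 3/5 D | 3/6 S |
| 5/10 D | 4/9 S | 4/10 S |

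After the same swap with replacement, 2/4, 3/6, 3/10 and 4/10 all stay at S.

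Three readings follow:
- At 3/4 and 4/6, removal without replacement still de-escalates; what is lost is the bar on returning to the dose.
- At 5/10, replacement gives a cell that meets the RP2D grid condition, which 5/10 does not.
- The 0/2 cell reads E, but Section 7.2.2.3 requires at least 3 patients per dose. Whether that minimum counts dosed or evaluable patients is not stated.

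**Illustration of outcome-dependent removal.** Suppose a share q of DLT patients is removed and replaced, and no DLT-free patient is removed. A counted patient then has DLT probability p(1−q)/(1−pq). For p = 0.40 and q = 0.20 this is 0.32/0.92 = 0.348. The documents give no value for q, so the range is assumed. The table gives the chance that a single reading at n = 10 is S or E (at most 4 DLTs):

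| True rate | q = 0 | 10% | 20% | 30% |
|---|---|---|---|---|
| 40% | 63.3% | 69.4% | 75.6% | 81.7% |
| 50% | 37.7% | 44.3% | 51.9% | 60.3% |

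**The case against.** Several points on the other side stand.

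- **The grid counts patients dosed.** Read literally, Sections 7.2.2.3 and 7.2.3 and Figure JNBA.1 keep every DLT in the count. A reader might infer that the plan plainly removes DLTs from escalation. The documents do not support that: they contain two counting rules and do not say which governs.
- **Timing.** A reader might also infer that the discretionary call is made once the outcome is known. Section 7.6.1 gives no timing. It permits this order of events but does not prescribe it.
- **Toxicity-caused deviations are protected.** A DLT that itself caused the noncompliance or the delay falls outside routes 2 and 3. The gap is a DLT alongside an unrelated deviation. It is less clear whether the qualifier in route 3 also covers reductions and omissions.
- **Noncompliance overlaps with discontinuation.** Section 6.3.1 lists noncompliance as a reason for discontinuation, and a patient discontinued in Cycle 1 comes under route 1 with its DLT exception. Route 2 still says the opposite for the same patient, so the overlap narrows the gap without closing it.
- **Replacement may be barred.** 7.6.1 stops replacement once accrual has stopped due to a DLT, which may apply at 2/3, 3/4, 4/6 and 5/10. The unreplaced column then applies and some changes are smaller.
- **Other safeguards.** The event stays in the safety summaries, escalation needs documented agreement, and a more conservative decision than the grid is allowed. These are real but do not restore the count. The DLT-equivalent check in Section 7.2.2.2 starts at Cycle 2, so it would not pick up the excluded event.
- **No direct conflict on delays.** The 7-day allowance defines protocol deviations and the 3-day limit defines evaluability. They serve different purposes. The overlap shows only that a permitted delay can open route 3.

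**Conclusion.** The gap is real and limited. Two of the three routes in Protocol 7.6.1 lack the DLT exception that the first one has, and the section does not agree with the escalation rules on which patients are counted. One removed DLT patient is enough to change the decision at several small counts, and at 5/10 with replacement it makes a failing dose meet the RP2D grid condition. Other cells do not move.

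A systematic push towards higher doses does not follow from the text alone. Removal unrelated to DLT status would leave the expected rate unbiased; the bias needs removal that depends on outcome, which the open-label discretionary rule allows. Its frequency is unknown, and the illustrated probabilities depend on the assumed q. The cell changes rest on Figure JNBA.1 itself; the assumed prior and cut-off serve only to reproduce it.

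**What to change.** 1. In Protocol 7.6.1, apply the existing DLT exception to every route to non-evaluability.
2. In Sections 7.2.2.3 and 7.2.3 and Figure JNBA.1, state that the grid counts DLT-evaluable patients, including every patient with a Cycle 1 DLT, at the assigned dose and schedule.
3. Document each evaluability decision, with its date, before the grid is read. List all excluded patients with their Cycle 1 AEs.
4. Mirror these definitions in SAP 6.3.

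Exclusion of DLT-free patients with deviations should not become mandatory. That could require more replacements, and keeping every DLT while always dropping DLT-free deviators would bias the rate upward.

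The cost is a few sentences in each document and a short exclusion listing. The downside is that the observed DLT rate at a dose may be slightly higher.

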8.1. Safety Evaluations

The safety and tolerability of LY3164530 have been assessed in nonclinical toxicology studies and this ongoing Phase 1 study. The results from these studies are detailed in the Investigator's Brochure. This Phase 1 study contains safety monitoring that will permit initial characterization of the safety profile of LY3164530 in patients with advanced or metastatic cancer. Study procedures and their timing, including collection of patient samples, are described in the Study Schedule ([Attachment 1](#)).

Standard laboratory tests will be performed as listed in [Attachment 2](#). A urine or serum pregnancy test will be administered to female participants, if applicable. Other clinical laboratory tests will also be collected. [Attachment 2](#) lists the specific tests that will be performed for this study.

8.1.1. Safety Data Collection and Review

Investigators are responsible for monitoring the safety of patients who have entered into this study and for alerting Lilly or its designee to any event that seems unusual, even if this event may be considered an unanticipated benefit to the patient.

The investigator is responsible for the appropriate medical care of the patient during the study.

The investigator remains responsible for following, through an appropriate health care option, AEs that are serious, considered related to study treatment or the study, or that caused the patient to discontinue before completing the study. The patient should be followed until the event is resolved, the event is no longer considered to be drug-related, the event becomes stable or returns to baseline, a new treatment is initiated for the patient, or the patient dies or is lost to follow-up. Frequency of AE and SAE follow-up evaluation is left to the discretion of the investigator, but must meet the minimum requirements outlined in [Table JNBA.5](#).

The timing of all safety evaluations is shown in the Study Schedule ([Attachment 1](#)). [Table JNBA.5](#) presents a summary of AE and SAE reporting guidelines. [Table JNBA.5](#) also shows which database or system is used to store AE and SAE data.

